The PIs, Site PI, and co-investigators will review any adverse events after each experiment to determine severity (serious or non-serious), expectedness (expected or unexpected) and relatedness (related, possibly related or unrelated). The study investigator will assess the relationship of any adverse event to be related or unrelated by determining if there is a reasonable possibility that the adverse event may have been caused by the study intervention.

To ensure consistency of adverse event causality assessments, investigators should apply the following general guideline when determining whether an adverse event is related:

Related: There is a plausible temporal relationship between the onset of the adverse event and the study intervention, and the adverse event cannot be readily explained by the participant's clinical state, intercurrent illness, or concomitant therapies; and/or the adverse event follows a known pattern of response to the study intervention; and/or the adverse event abates or resolves upon discontinuation of the study intervention or dose reduction and, if applicable, reappears upon re-challenge.

Possibly Related: Possibly related to the research means there is a reasonable possibility that the adverse event, incident, experience or outcome may have been caused by the procedures involved in the research (modified from the definition of associated with use of the drug in FDA regulations at 21 CFR 312.32(a)). Reasonable possibility means that the event is more likely than not related to participation in the research or, in other words, there is a $>50\%$ likelihood that the event is related to the research procedures

Not Related: Evidence exists that the adverse event has an etiology other than the study intervention (e.g., preexisting medical condition, underlying disease, intercurrent illness, or concomitant medication); and/or the adverse event has no plausible temporal relationship to study intervention.

Serious adverse event means any event temporally associated with the participant's participation in research that meets any of the following criteria:

- results in death
- is life threatening (places the participant at immediate risk of death from the event as it occurred)
- requires inpatient hospitalization or prolongation of existing hospitalization;
- results in a persistent or significant disability/incapacity
- results in a congenital anomaly/birth defect

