9.3.2 Reporting Guidelines

Any serious adverse events or unexpected but related or possibly related adverse events will be communicated to the PIs as soon as possible and within 48 hours of the time they are detected. Adverse events will be reported promptly to the IRB, the DSMB, and Beta Bionics. Beta Bionics is the sponsor of the Investigational Device Exception (IDE) for the bionic pancreas to be used in this trial. Reports of adverse events will be made to the FDA in compliance with the terms of IDE.

10 Participant Compensation

Financial compensation will be provided to all participants who complete the screening visit. Participants will be paid \$25 for completing the screening visit whether or not they are eligible to participate in the study. Study participants will be compensated per the following schedule.

	Screening	Cross over: Usual Care			Cross over: Bionic Pancreas		
		Day 1	Mid Period Follow-up	Crossover/Day 1	Mid Period Follow-up	Final Visit	
Visit 1	Visit 2	Visit 3	Visit 4	Visit 5	Visit 6	Visit 7	Visit 8
Screening	\$25						
Visit Stipend		\$50			\$50		\$50
Mid-period follow-up			\$20	\$20		\$20	\$20
Questionnaire Completion		\$25			\$25		\$25

The total compensation for a participant who completed all study visits and questionnaires would be \$330.

Parking/transportation expenses will be paid for up to \$30 per participant for each visit.

Participants who are unable to complete the study or choose to stop participation will receive prorated compensation for the portion of the study visits that they complete.

11 References

1. Diabetes Control and Complications Trial Research Group et al. "The effect of intensive treatment of diabetes on the development and progression of long-term complications in insulin-dependent diabetes mellitus." *The New England journal of medicine* vol. 329,14 (1993): 977-86. doi:10.1056/NEJM19930930291401
2. Nathan, David M et al. "Intensive diabetes treatment and cardiovascular disease in patients with type 1 diabetes." *The New England journal of medicine* vol. 353,25 (2005): 2643-53. doi:10.1056/NEJMoa052187

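### The >50% bar for possibly related in 9.3.1 leaves some plausible adverse events unclassified, so non-serious unexpected ones can miss the 48-hour notice to the PIs

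*Combined protocol and SAP*

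**What the plan says.** All of this stands in the combined protocol and SAP, section 9.3.

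- **Categories.** In 9.3.1 the investigators review adverse events after each experiment and sort relatedness into three classes: related, possibly related or unrelated.
- **A two-way rule.** The next sentence uses two classes only: "The study investigator will assess the relationship of any adverse event to be related or unrelated by determining if there is a reasonable possibility". The possibility meant is causation by the study intervention.
- **Related.** Three alternatives are joined by and/or, and no likelihood is attached to any of them. The first is plausible timing where "the adverse event cannot be readily explained by the participant's clinical state, intercurrent illness, or concomitant therapies". The second needs only this: "the adverse event follows a known pattern of response to the study intervention". The third is improvement when the intervention is stopped or reduced.
- **Possibly related.** A reasonable possibility of causation by the research procedures, with this gloss: "Reasonable possibility means that the event is more likely than not related to participation in the research". The sentence then restates the bar as a likelihood above 50%.
- **Not related.** One criterion is "Evidence exists that the adverse event has an etiology other than the study intervention". The alternative, enough by itself, is that "the adverse event has no plausible temporal relationship to study intervention".
- **Trigger.** In 9.3.2: "Any serious adverse events or unexpected but related or possibly related adverse events will be communicated to the PIs". The limit is 48 hours from detection.

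**The concern.** Three categories that steer reporting should between them cover every event. Here the category that sounds weakest, *possibly related*, is the only one with a probability bar, and the bar is set above one half. *Not related* is not simply what remains: it has its own positive requirements. That opens a space between the two.

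The phrase *reasonable possibility* also does two jobs. In the two-way sentence it separates related from unrelated; in the three-way list it defines *possibly related*. The section says its guideline exists to make causality assessments consistent, yet two investigators could both follow it and label the same event differently.

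At stake is how quickly an uncertain, non-serious, unexpected event reaches the PIs. Section 1.1 says iLet results so far come only from endocrinologists giving in-person care, and section 8 describes the other care models as untested. Uncertain attribution is to be expected there. Section 9.2 suspends the study for a safety issue seen in multiple participants, and with two sites such a pattern is easier to notice if events reach the PIs promptly.

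**Working it through.** No arithmetic applies. The 50% figure is a definition rather than a result, and there is no plan figure to reproduce. The check has two parts: whether the three definitions cover every case, and which events depend on relatedness for the 48-hour trigger.

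**Step 1. Test events.** Take events with plausible timing and a judged likelihood of 50% or less. All of them fail *possibly related* by its own bar. Set them against the other two definitions:

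| Event | Related? | Not related? | Result |
|---|---|---|---|
| A. No ready alternative explanation | Yes, first criterion | No | Related |
| B. Known response pattern, or resolves on stopping | Yes, either criterion alone is enough (and/or) | Not needed | Related |
| C. Ready alternative explanation, with evidence for it; none of B | No | Yes, first criterion | Not related |
| D. Ready alternative explanation, no evidence for it; none of B | No | No: no evidence, and timing is plausible | None |

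The gap is D.

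**Step 2. The two-way sentence.** Assume that *reasonable possibility* means the same in both places, so above 50%. Event D then becomes unrelated, although neither criterion for *not related* is met. Event A, if judged at 50% or less, is unrelated under the two-way sentence and related under the list. The two rules cannot both be followed.

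**Step 3. The 48-hour trigger in 9.3.2.** Cross seriousness with expectedness (2 × 2 = 4 cells):

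| | Expected | Unexpected |
|---|---|---|
| Serious | Triggered whatever the relatedness | Triggered whatever the relatedness |
| Non-serious | Not triggered in any relatedness class | Triggered only if related or possibly related |

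Only one cell of the four, non-serious and unexpected, depends on relatedness. An event D in that cell, whether unclassified or labelled unrelated, is not triggered.

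**Step 4. Other routes for that cell.**
- 9.3.2 also sends adverse events to the IRB, the DSMB and the device company promptly, with no relatedness condition and no limit in hours.
- 9.2 tells the DSMB of unanticipated adverse device events.
- 9.2 also has a 72-hour DSMB rule for events described as serious and unexpected. It is unclear whether an event must be both or either. If either, event D in this cell reaches the DSMB within 72 hours.
- 9.3.1 has the PIs review adverse events after each experiment.

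**Step 5. Results that use relatedness.** The safety endpoints in 6.4 are frequencies of adverse events, severe hypoglycemia and DKA. Section 6.7.1 defines treatment-emergent events by onset date and plans descriptive summaries only. None of these depends on relatedness.

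**The case against.** The strongest reply is that the gap is narrow and well backed up. *Related* has no probability bar and captures many events at or below 50%. The alternative causes listed under *related* and *not related* largely mirror each other, so a ready explanation will often count as evidence of another cause, which moves event D into C. The text calls itself a general guideline, so an investigator would use judgement rather than leave a case unlabelled. Other safeguards ignore relatedness: events are queried at every visit after screening (Schedule of Visit Procedures), participant contacts are documented (5.7.2), the site PI hears within one hour of calls about ketosis concerning for DKA or severe hypoglycemia (5.7.4), and the pause rule for those events uses no relatedness class (9.2).

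Most of this stands, and it limits the point. It does not close it: a ready explanation is not always evidence, the two rules still contradict each other, and the 48-hour sentence still depends on the label.

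Three stronger readings are tempting and are not supported:
- *Every event at or below 50% lacks a category.* Events A to C show otherwise.
- *Uncertain events escape expedited reporting.* Serious events reach the PIs within 48 hours regardless. For the rest, the supportable consequence is possible delay to the PIs, not loss.
- *Device-related events are bound to be under-counted, and the safety results with them.* *Related* can be met by a known pattern alone, whatever the judged likelihood, which pushes the other way; and no planned endpoint counts related events.

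**Conclusion.** The point holds in a narrow form: wrong as written, minor in severity. The >50% definition leaves a residue of plausible events that meet none of the three definitions, and it conflicts with the two-way sentence, which would call them unrelated without the required evidence. The consequence is confined to non-serious, unexpected events that may miss the 48-hour communication to the PIs. How many there would be cannot be derived from the documents.

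This rests on three assumptions: the definitions are applied as written; *reasonable possibility* carries one meaning throughout 9.3.1; and a ready alternative explanation does not by itself amount to evidence of another cause. If the third were relaxed, the residue would shrink, but the conflict between the two rules would remain.

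**What to change.** In 9.3.1:
1. Remove the sentence that equates reasonable possibility with more likely than not and above 50%.
2. State that any event with plausible timing that meets neither *related* nor *not related* is classed as *possibly related*. The categories are then exhaustive: without plausible timing an event is already *not related*, and with it one of the three must apply.
3. Rewrite the two-way sentence to use the same three categories.

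In 9.3.2, keep related or possibly related as the trigger for unexpected events.

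The cost is a wording amendment and a few more non-serious events labelled *possibly related* and, where unexpected, communicated within 48 hours. Design, sample size, treatment and endpoints do not change. The residual rule goes no further than closing the gap: events with evidence of another cause can still be classed as *not related*.

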9.3.2 Reporting Guidelines

Any serious adverse events or unexpected but related or possibly related adverse events will be communicated to the PIs as soon as possible and within 48 hours of the time they are detected. Adverse events will be reported promptly to the IRB, the DSMB, and Beta Bionics. Beta Bionics is the sponsor of the Investigational Device Exception (IDE) for the bionic pancreas to be used in this trial. Reports of adverse events will be made to the FDA in compliance with the terms of IDE.

10 Participant Compensation

Financial compensation will be provided to all participants who complete the screening visit. Participants will be paid \$25 for completing the screening visit whether or not they are eligible to participate in the study. Study participants will be compensated per the following schedule.

	Screening	Cross over: Usual Care			Cross over: Bionic Pancreas		
		Day 1	Mid Period Follow-up	Crossover/Day 1	Mid Period Follow-up	Final Visit	
Visit 1	Visit 2	Visit 3	Visit 4	Visit 5	Visit 6	Visit 7	Visit 8
Screening	\$25						
Visit Stipend		\$50			\$50		\$50
Mid-period follow-up			\$20	\$20		\$20	\$20
Questionnaire Completion		\$25			\$25		\$25

The total compensation for a participant who completed all study visits and questionnaires would be \$330.

Parking/transportation expenses will be paid for up to \$30 per participant for each visit.

Participants who are unable to complete the study or choose to stop participation will receive prorated compensation for the portion of the study visits that they complete.

11 References

1. Diabetes Control and Complications Trial Research Group et al. "The effect of intensive treatment of diabetes on the development and progression of long-term complications in insulin-dependent diabetes mellitus." *The New England journal of medicine* vol. 329,14 (1993): 977-86. doi:10.1056/NEJM19930930291401
2. Nathan, David M et al. "Intensive diabetes treatment and cardiovascular disease in patients with type 1 diabetes." *The New England journal of medicine* vol. 353,25 (2005): 2643-53. doi:10.1056/NEJMoa052187

12.1 Appendix A: Prior Bionic Pancreas Studies

Prior studies utilizing the Bionic Pancreas are summarized herein. Relevant citations are included in a reference list at the end of the document.

12.1.1 *iPhone-Based BP Outpatient Studies*

Subsequent to our past preclinical studies (2005–2009) at BU that used a diabetic swine model and our inpatient clinical trials (2008–2012) in the Clinical Research Center at MGH, we began our outpatient clinical studies using the iPhone-based BP.

[figure not shown]
12.1.2 *The Beacon Hill Study, the 2013 and 2014 Summer Camp Studies, and the Bionic Pancreas Multi-Center Study*

In 2013, we conducted our first outpatient study, which we refer to as the Beacon Hill Study (2013), and which followed a random-order cross-over design in which 20 adults (≥ 21 y) with T1D, with 5 days on the BP and 5 days of usual care. In the usual-care control arm, participants used insulin pump therapy (and their CGM if applicable), and they wore a CGM with blinded display and muted alarms. In the BP arm, participants kept to a three-square-mile geographic area centered around the Beacon Hill neighborhood in Boston. They ate freely at restaurants and exercised at will with access to two gyms. Analysis was pre-specified to Days 2–5, since glycemic control is more representative of BP performance after most of the adaptation by the BP occurs on Day 1. Results are summarized in the plots of Figure 2. Results of the Beacon Hill Study were included in a 2014 article published in the *New England Journal of Medicine*.

In parallel, we conducted the 2013 Summer Camp Study, which followed a random-order cross-over design in which 32 adolescents with T1D participated, with 5 days on the BP and 5 days of supervised camp care in the control arm. In the control arm, participants used conventional insulin pump therapy (and their CGM if applicable) and wore the BP without pumps (to enable remote monitoring). All participants were monitored remotely for CGM glucose < 70 mg/dl lasting more than 15 minutes, which prompted potential treatment by the study staff. Participants were fully integrated into normal camp activities without restrictions on diet or exercise. The mean HbA1c of all 32 participants at baseline (pre-study) was 8.2%, which corresponds to a mean BG of 189 mg/dl. Results are summarized in the plots of Figure 2. Results of the 2013 Summer Camp Study were included in a 2014 article published in the *New England Journal of Medicine*.

In 2014, we conducted our 2014 Summer Camp Study, in pre-adolescents 6–11 years old with T1D. The study was of similar in design to our 2013 Summer Camp Study. Results are summarized in the plots of Figure 2. Results of the 2014 Summer Camp Study were published in 2016 in *The Lancet Diabetes & Endocrinology*.

Also in 2014, we conducted our first home-use study, testing the BP in adults (≥ 18 y) with T1D. The study is referred to as the Bionic Pancreas Multi-Center study and followed a random-order cross-over design in which 39 adults participated in 11 days on the BP and 11 days of usual care. Participants went to work as usual, and lived and slept at home, all without clinical supervision. There were no restrictions placed on diet or exercise. The study included four medical centers (10 participants per center), namely MGH, the University of Massachusetts Medical School, Stanford University, and the University of North Carolina at Chapel Hill. Results are summarized in the plots of Figure 2. Results of the Multi-Center were published in 2016 in *The Lancet*.

2014 Summer Camp Study

BP Multi-Center Study

[figure not shown]

Figure 2. Outpatient summary results of mean CGM glucose levels and hypoglycemia in the bihormonal BP and control arms from the Beacon Hill Study, 2013 and 2014 Summer Camp Studies, and the Bionic Pancreas Multi-Center Study. Mean CGM level for each participant under usual care (red circle on the left) is connected with their mean CGM level on the BP (black circle on the right). The circle diameter is proportional to % CGM values <60 mg/dl. The bold circles and lines represent group means. The horizontal red dashed line refers to the glucose level corresponding to the ADA therapy goal for that age group at that time, which corresponds to 154 mg/dl (HbA1c < 7%) for adults and 169 mg/dl (HbA1c < 7.5%) for children (the ADA target has since been unified to be HbA1c < 7% (mean glucose <154 mg/dl) for all age groups).

12.1.3 The Bionic Pancreas Set Point Study

In 2015, we conducted our MGH Set-point Study, where we tested the BP at different static glucose targets (“set-points”) in both the bihormonal and insulin-only configurations. Twenty 20 adults participated in 7 study arms, each lasting 3 days. Unlike preceding studies where the target glucose for the bihormonal BP was set to 100 mg/dl, glucose targets of 100, 110, 130 mg/dl were studied in the bihormonal configuration and 110, 120, 130, and 145 mg/dl were studied in the insulin-only configuration. Results are summarized in Figure 3. Based on the study results, we determined that a default glucose target of 110 mg/dl for the bihormonal configuration and 120 mg/dl for the insulin-only configuration strike optimal balance between minimizing mean glucose and hypoglycemia while maximizing patient satisfaction.

[figure not shown]

Figure 3. Summary results from the Bionic Pancreas Set-Point Study. Left: Outpatient results summarizing the distribution of mean CGM levels and hypoglycemia in the insulin-only BP arms (with set-points 130, 120, and 110 mg/dl) and usual-care arm (control). Right: Outpatient results summarizing the distribution of mean CGM glucose levels and hypoglycemia in the bihormonal BP arms (with set-points of 130, 110, and 100 mg/dl) and usual-care arm (control). Mean CGM levels for each participant in each study arm (red circles) are connected by black lines. The circle diameter is proportional to % of CGM values <60 mg/dl. The heavy circles and lines represent the group means. The horizontal red dashed line refers to the ADA therapy goal, which corresponds to 154 mg/dl (HbA1c < 7%) for adults with T1D ≥ 18 years old.

12.1.4 The Stanford Insulin-Only Study

In 2015, we conducted the Stanford Insulin-Only Study, where 16 adults participated in a week of usual care followed by a week on the insulin-only BP, where a target glucose of 130 mg/dl was initiated and potentially lowered to 115 mg/dl if certain criteria were met. Participants were monitored remotely for CGM glucose <50 mg/dl lasting more than 15 minutes, which prompted a call by the study staff. Results of the study are summarized in Figure 5.

[figure not shown]

Figure 4. Outpatient results summarizing the distribution of mean CGM glucose levels and hypoglycemia in the insulin-only BP and control arms from the Stanford Insulin-Only Study. Mean CGM levels for each participant in each study arm (red circles) are connected by black lines. The circle diameter is proportional to % of CGM values < 60 mg/dl. The heavy circles and lines represent the group means. The horizontal red dashed line refers to the ADA therapy goal, which corresponds to 154 mg/dl ($HbA1c < 7\%$) for adults with $T1D \geq 18$ years old.

12.1.5 The Bionic Pancreas Monitoring Study

In 2016, we conducted the Monitoring Study, where we tested the prospects of removing remote telemetric monitoring for severe biochemical hypoglycemia by testing the bihormonal BP at a target of 100 mg/dl, the insulin-only BP at a target 110 mg/dl, and usual care, each two 7-day arms, one with and the other without remote telemetric monitoring for hypoglycemia (total of 6 study arms). The results are summarized in Figure 6. There was more hypoglycemia without monitoring relative to with monitoring in the two usual-care arms (1.95 versus 1.32%, $p=0.02$), but no difference in hypoglycemia without monitoring relative to with monitoring in the two bihormonal BP arms (0.99 versus 1.05%, $p=0.82$) and two insulin-only BP arms (1.66 versus 1.55%, $p=0.74$) arms. We concluded that remote telemetric monitoring had no effect on hypoglycemia with the BP, and could be safely omitted from future studies.

[figure not shown]

Figure 5. Outpatient results summarizing the distribution of mean CGM glucose levels and hypoglycemia in the insulin-only BP and control arms from the Bionic Pancreas Monitoring Study. Mean CGM levels for each participant in each study arm (red circles) are connected by black lines. The circle diameter is proportional to % of CGM values < 60 mg/dl. The heavy circles and lines represent the group means. The horizontal red dashed line refers to the ADA therapy goal, which corresponds to 154 mg/dl (HbA1c <7%) for adults with T1D \geq 18 years old.

12.1.6 iPhone BP System Studies

Year	Name of Study	Setting, Date span	Cohort studied	Duration & device exposure*	Configuration & Set Points	Medications used	Protocol Description, Outcome, if applicable.	Result: Mean CGM, % CGM < 60 mg/dl
2013	Beacon Hill	Supervised hotel stay	20 adults aged ≥21	5 days 2,400 hours	Bihormonal 100 mg/dl iPhone and two Tandem t:slim pumps	Insulin lispro (Eli Lilly) Glucagon (Eli Lilly)	RCT with usual care at home Direct supervision	BP: 133±13 mg/dl, 1.5% UC: 158±30 mg/dl, 3.7%
2013	2013 Summer Camp	Supervised summer setting	32 adolescents aged 12–18	5 days 3,840 hours	Bihormonal 100 mg/dl iPhone and two Tandem t:slim pumps	Insulin lispro (Eli Lilly) Glucagon (Eli Lilly)	RCT with usual care at camp Remote telemetric monitoring	BP: 142±12 mg/dl, 1.3% UC: 158±27 mg/dl, 2.2%
2014	2014 Summer Camp	Supervised camp setting	19 pre-adolescents aged 6–11	5 days 2,280 hours	Bihormonal 100 mg/dl iPhone + two Tandem t:slim pumps	Insulin lispro (Eli Lilly) Glucagon (Eli Lilly)	RCT with usual care at camp Remote telemetric monitoring	BP: 137±11 mg/dl, 1.2% UC: 168±30 mg/dl, 2.8%
2014	BP Multi-center	Outpatient, home, 4 study sites	39 adults aged ≥18	11 days 10,296 hours	Bihormonal 100 mg/dl iPhone and two Tandem t:slim pumps	Insulin lispro (Eli Lilly) Insulin aspart (Novo Nordisk) Glucagon (Eli Lilly)	RCT with usual care Remote telemetric monitoring	BP: 141±10 mg/dl, 0.6% UC: 162±29 mg/dl, 1.9%
2015 - 2016	BP Set Point	Outpatient, unsupervised at home	20 adults aged ≥18	8 arms, 4 days each 15,360 hours	Bihormonal and Insulin-only Bihormonal: 100, 110, 115, 130 mg/dl Insulin-only: 110, 120, 130, 145 mg/dl iPhone and one or two Tandem t:slim pumps	Insulin lispro (Eli Lilly) Insulin aspart (Novo Nordisk) Glucagon (Eli Lilly)	RCT with usual care and 8 different BP configurations testing different glucose target set points in addition to insulin only for the first time Both configurations at 110 mg/dl and 130 mg/dl included an exercise challenge to induce hypoglycemia under direct observation in the clinic Results helped identify the glucose target settings that will be used in future studies. These were set to range from 110 mg/dl to 130 mg/dl, with a default of 120 mg/dl in the insulin-only configuration, and set to range from 100 mg/dl to 120 mg/dl, with a default of 110 mg/dl in the bihormonal	Bihormonal: 100 mg/dl: 136±14 mg/dl, 0.8% 110 mg/dl: 148±17 mg/dl, 0.4% 115 mg/dl: 146±15 mg/dl, 0.9% 130 mg/dl: 156±12 mg/dl, 0.5% Insulin-only: 110 mg/dl: 153±15 mg/dl, 1.3% 120 mg/dl: 156±15 mg/dl, 1.1% 130 mg/dl: 161±17 mg/dl, 0.8% 145 mg/dl: 174±23 mg/dl, 1.0% UC: 158±31 mg/dl, 1.4%

							configuration	
							Remote telemetric monitoring	
2015 - 2016	Stanford Insulin-only IDE: G150142 JUL-2015	Outpatient, unsupervised at home Start-End: 10-2015–01-2016	16 adults aged ≥ 18	2 arms, days each 5,376 hours	7 Insulin-only 115 to 130 mg/dl iPhone and one Tandem t:slim pump	Insulin lispro (Eli Lilly) Insulin aspart (Novo Nordisk)	RCT with usual care Results helped identify the glucose target settings that will be used in future studies Remote telemetric monitoring	BP: 160 \pm 9 mg/dl, 0.9% UC: 151 \pm 26 mg/dl, 1.9%
2017	Monitoring IDE: G150130 JUL-2015	Outpatient, unsupervised at home Start-End: APR-2017–MAY-2017	23 adults aged ≥ 18	4 arms, days each 15,456 hours	7 Bihormonal and Insulin-only Biormonal: 100 mg/dl Insulin-only: 110 mg/dl iPhone and one or two Tandem t:slim pumps	Insulin lispro (Eli Lilly) Insulin aspart (Novo Nordisk) Glucagon (Eli Lilly)	RCT with one usual care arm and two BP arms, each repeated with and without remote monitoring Each arm repeated with and without remote telemetric monitoring Results confirmed that the insulin-only and bihormonal BP set at their lowest targets (110 and 100 mg/dl, respectively) are safe to be used in outpatient setting without remote monitoring for hypoglycemia	With monitoring: Insulin-only: 151 \pm 13 mg/dl, 1.6% Biormonal: 139 \pm 13 mg/dl, 1.0% UC: 164 \pm 29 mg/dl, 1.3% Without monitoring: Insulin-only: 148 \pm 11 mg/dl, 1.7% Biormonal: 139 \pm 11 mg/dl, 1.0% UC: 165 \pm 29 mg/dl, 2.0%
2016 - 2017	Zealand Feasibility Study IDE: G160012 FEB-2016	Supervised, in clinic Start-End: 12-2016–03-2017	10 adults aged ≥ 18	2 arms, hours each 160 hours	8 Biormonal 100 mg/dl iPhone and two Tandem t:slim pumps	Insulin lispro (Lilly) Insulin aspart (Novo Nordisk) Glucagon, 1 mg/ml (Lilly) Dasiglucagon, 1 mg/ml (Zealand)	RCT comparing Eli Lilly glucagon with dasiglucagon in clinic setting BP was challenged with participants wearing their own insulin pump in addition to the BP insulin dosing, with up to two times their normal basal running and a full meal bolus via their own pump. There was an exercise challenge in the late post-prandial period Direct supervision	Dasiglucagon: 110 \pm 29 mg/dl, 13% Lilly glucagon: 99 \pm 22 mg/dl, 20%

*Total device exposure is calculated based on cohort size used in the final study analysis

12.1.7 *iLet Outpatient Studies*

The studies described below used the Gen 3 iLet and either the G5 Dexcom CGM or Senseonics Eversense CGM. The Insulin-Only Bionic Pancreas Pivotal Trial will use the Gen 4 iLet with the G6 Dexcom CGM.

12.1.8 *The iLet Insulin-Only Bionic Pancreas Bridging Study*

In 2018, the Adult RCT phase of the iLet Insulin-only Bridging Study was conducted as a random-order,

cross-over, home-use trial that compared the insulin-only iLet using lispro or aspart to the insulin-only iLet using Fiasp to usual care (UC) for 7 days each. The study enrolled 12 subjects who used MDI therapy and 22 subjects who used insulin pump for their UC. Participants at MGH ($n = 17$) used the Senseonics Eversense CGM while those at Stanford ($n = 17$) used the G5 Dexcom CGM as the input CGM to the iLet. This is the only automated insulin delivery study to test (1) two CGM devices, (2) an ultra-rapid insulin analog, and (3) a cohort including MDI and insulin pump users. Since only body weight is required to initialize the iLet, and no information is required about either insulin therapy regimen, the iLet is the only device that undergo this test without a run-in period to first determine a baseline pump therapy regimen. The iLet is ideally suited for use in underserved or insulin-pump-naïve populations, as well as in populations where endocrinologists and diabetologists are not available or are in short supply. The iLet performed equally well on MDI and insulin pump therapy subjects. Results are summarized in Figure 7.

[figure not shown]

Figure 6. Distribution of mean glucose and hypoglycemia in the Insulin-Only Bionic Pancreas Bridging Study. Mean CGM glucose level for each subject is shown over Days 3–7 under usual care, on the insulin-only iLet in using lispro or aspart, and on the insulin-only iLet using Fiasp. The mean CGM glucose and % CGM values <60 mg/dl were respectively 163 ± 26 mg/dl and 1.3% under usual care, 155 ± 13 mg/dl and 1.2% with the iLet using lispro or aspart, and 154 ± 11 mg/dl and 1.3% with the iLet using Fiasp. Red lines and circles correspond to MDI subjects and blue lines and circles correspond to insulin-pump therapy users.

